#### **b. Procedure**

Speech perception tests will be conducted:

- Preoperatively, on both ear with the best fitted hearing aid(s), and
- Postoperatively, on ipsilateral ear with activated CIS and an occluded contralateral ear with ear-plug.

Ear-plugs will be supplied for all centers.

#### **At visit 2 (preoperatively)**

The test is conducted in quiet and in noise background, and in the best-aided conditions

In quiet:

The subject's is given practice sentences to become familiar with the task before each test. Then two 20-sentences lists of HINT shall be presented to the subject, in front (0° azimuth), in quiet at a conversational speech level of 60 dB SPL (Appendix 9: Calibration considerations). All words in the sentence repeated correctly, (Nilsson et al. 1994 [5]) shall be computed to calculate a score in percent correct of total words.

In noise:

As described above, the same procedure is applied for HINT-N, sentences are presented at +10dB SNR, with noise set at 55 dB SPL, and signal at 65 dB SPL.

#### **From visits 6 to 8 (postoperatively)**

The tests shall be measured in quiet and in noise. Measurements are performed in the ipsilateral ear with an occluded contralateral ear with ear-plug

In quiet and in noise, similar conditions of the test are used as described in visit 2.

Speech perception score are computed to calculate score in percent correct (%)

#### **c. HINT score calculation in quiet and noise conditions**

The ratio of words correctly repeated divided by the total of words for each list is multiplied by 100 to obtain the score in percent correct for the lists.

#### **3.5.5.2 Procedures to Assess Safety**

For the timing assessment please refer to the schedule of activities in section 3.5.5.4.

The PI shall be responsible for safety data collection.

The PI may plan any unscheduled consultations as needed to follow any adverse event.

All complications/adverse events are recorded and classified as major or minor complication by the investigator.

Serious Adverse Event or Major Complication (related or not related to the device) are those that are life-threatening (e.g. meningitis, death), those requiring hospitalization and/or resulting in disability or permanent damage (e.g. permanent facial nerve paresis, permanent chorda tympani syndrome, permanent vertigo/dizziness, persistent pain discomfort requiring device explant), those requiring revision surgery with or without re-implantation (e.g. device explant, surgery to prevent permanent impairment, large scalp necrosis, severe infection, electrode shifting, eardrum perforation, receiver positioning and cholesteatoma) and tinnitus, facial stimulation, pain that could not be alleviate by electrode deactivation; and other serious medical events.

Adverse Event or Minor Complication (related or not related to device) are those that resolve spontaneously without surgical intervention (e.g. wound infection treated by antibiotics; skin flap hematoma; transient or rising tinnitus; transient vertigo/dizziness; transient pain; transient chorda tympani syndrome; transient facial nerve palsy, and tinnitus, facial stimulation and pain that could be relieved by electrode deactivation), or with conservative medical management (medical complications, pre-existing conditions such otitis media).

All explanted devices returned to the manufacturer will be classified according the AAMI-CDV-4 CI86 guideline, and ditto for the non-implantable part (i.e. sound processor, accessories).

### **Description**

All adverse events and serious adverse events related to surgical/medical procedures and/or device shall be collected from the time subject is implanted till the completion of the study and shall also include any unscheduled visits dealing with adverse events or serious adverse events.

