#### **2.4.1.2 Safety: Major Complications**

Occurrence of major complications in all participants suffering from severe to profound bilateral sensorineural hearing loss and for whom an implantation of the device was initiated will be the co-primary objective. All surgical and device-related events will be reported and the number and proportion of major complications will be estimated.

Safety data will be collected from the preoperative visit (during surgical procedure) to the end of patient participation.

Adverse events or complications will be classified as medical/surgical or device related. Complications will be classified as major if they require surgical intervention and minor if they resolve spontaneously or with non-invasive medical treatment categories [12,22,23].

Any device failure will be investigated and classified according to AAMI-CDV-4 CI86 guideline for Cochlear Implants.

A list of adverse events is defined in section 4.2. Unanticipated adverse events (section 4.5.8) may occur (not listed in 4.2) and like anticipated events they will be reported, followed and classified.

Occurrence of major complications will be a co-primary endpoint and the presentation of the safety profile (all adverse events reported) will be a secondary objective and mainly descriptive. Incidence rate of minor and major complications will be estimated globally and per categories in order to describe the device safety profile. Data from literature on currently similar devices FDA approved will be used as yardsticks.

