### **c) Safety Analysis Set (SAS)**

It consists of all subjects for whom surgery for implantation started.

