### **4.5 Adverse Event Recording/Reporting**

#### **4.5.1 Adverse Events**

All observed or volunteered adverse events regardless of investigational device or suspected causal relationship to the investigational device shall be reported as described in the following sections.

For all adverse events, the investigator shall pursue and obtain adequate information both to determine the outcome of the adverse event and to assess whether it meets the criteria for classification as serious adverse events (see section 4.5.6) requiring immediate notification of Oticon Medical or its designated representative. For all adverse events, sufficient information shall be obtained by the investigator to determine the causality of the adverse event. The investigator shall be required to assess causality. For adverse events with a causal relationship to the investigational device, follow-up by the investigator shall be required until the event or its sequelae resolve or stabilize at a level acceptable to the investigator and Oticon Medical concurs with that assessment.

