#### **4.5.2 Reporting Period**

Serious adverse events require immediate notification of Oticon Medical or its designated representative beginning from the time that the subject provides informed consent, which is obtained prior to the subject's participation in the clinical trial, i.e. prior to undergoing any trial related procedure and/or receiving investigational device, up to and including 28 calendar days after last visit. Any serious adverse event occurring any time after the reporting period must be promptly reported if a causal relationship to the investigational device is suspected.

Adverse events (serious and non-serious) should be recorded on the CRF from the time the subject has been implanted through 28 calendar days following the last subject visit.

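### Two protocol sections start adverse-event recording at implantation although the safety set starts at surgery, and the sections also disagree on causality scope and end date

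*Protocol*

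**What the plan says.** **Start of recording.** Protocol 3.5.5.2 (Description) says that "serious adverse events related to surgical/medical procedures and/or device shall be collected from the time subject is implanted till the completion of the study". Section 4.5.2 says that "Adverse events (serious and non-serious) should be recorded on the CRF from the time the subject has been implanted through 28 calendar days" after the last visit. The same section starts immediate notification of serious events to the sponsor much earlier, "beginning from the time that the subject provides informed consent". Section 2.4.1.2 says: "Safety data will be collected from the preoperative visit (during surgical procedure) to the end of patient participation"; SAP 5.9 repeats this. The schedule in 3.5.5.4 marks adverse-event reporting at the surgery visit. The Visit 3 list in 3.5.7, section 3.6.1.1 b) and the Visit 3 data list in SAP 2.1 also cover the operation.

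**Safety population.** For the Safety Analysis Set, protocol 3.6.2.1 c) says: "It consists of all subjects for whom surgery for implantation started". SAP 4.3 agrees, and 2.4.1.2 and 3.6.2.3 define the co-primary safety population in the same way. The Full Analysis Set in 3.6.2.1 a) is limited to subjects who were implanted.

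**Causality scope.** Against the wording in 3.5.5.2 (Description), section 4.5.1 says: "All observed or volunteered adverse events regardless of investigational device or suspected causal relationship to the investigational device shall be reported". Earlier in 3.5.5.2 itself, the definition begins: "Serious Adverse Event or Major Complication (related or not related to the device) are those that are life-threatening".

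**End of recording.** Three ends are given: completion of the study (3.5.5.2, Description), the end of the patient's participation (2.4.1.2, SAP 5.9), and 28 days after the last visit (4.5.2).

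**The concern.** The numerator and the denominator of the co-primary safety rate should open at the same moment. The plan itself separates a subject whose surgery has started from a subject who is implanted, since that is the difference between the safety set and the Full Analysis Set. A subject whose operation is started and then abandoned is in the first set and not in the second. Neither document says how adverse events are recorded for that subject. Protocol 4.2 names anesthesia reactions, facial-nerve injury and cerebrospinal fluid leakage as risks of the procedure, so an intra-operative complication is foreseeable. If it is not entered on the adverse-event form, only the numerator shrinks.

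The scope conflict is a separate matter. It bears on the any-adverse-event rate (protocol 3.6.2.4 g) and on the tabulation of device-related against unrelated events (SAP 6.4). Sites that read the scope differently would supply counts that are not comparable.

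**Working it through.** **1. The rules side by side.**

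| Item | Later or narrower rule | Earlier or wider rule |
|---|---|---|
| Start | Once implanted: 3.5.5.2 Description; 4.5.2 (form recording) | During surgery: 2.4.1.2, 3.5.5.4, 3.5.7 Visit 3, 3.6.1.1 b), SAP 2.1, SAP 5.9. From consent: 4.5.2 (serious-event notification only) |
| Denominator | – | Surgery started: 2.4.1.2, 3.6.2.1 c), 3.6.2.3, SAP 4.3 |
| Scope | Procedure- or device-related: 3.5.5.2 Description | Regardless of cause: 4.5.1. Major complications related to the device or not: 3.5.5.2 |
| End | Study completion, or end of participation | 28 days after last visit: 4.5.2 |

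**2. A started but abandoned implantation.** The subject is in the safety set. Under 2.4.1.2 and the schedule, the complication is recorded. Under the literal wording of 3.5.5.2 (Description) and 4.5.2, no adverse-event form entry is due, because the subject was never implanted. Causality makes no difference here: the event is related to the surgery, so it satisfies both the wording in 3.5.5.2 and the definition of a complication in SAP 5.6.2.

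**3. The plan's own safety figures** (protocol 3.6.1.4, SAP 1.3; N = 50, rate 2%).
- Chance of at least one event: 1 − 0.98^50 = 0.636, against the stated 63.5%.
- Exact (Clopper-Pearson) 95% upper limit at 1/50: the p that solves (1 − p)^50 + 50p(1 − p)^49 = 0.025, which is 10.65%, against the stated 10.6%.

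Both reproduce.

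**4. Effect of one missed major complication (hypothetical).** Exact upper limits; with no events the limit is 1 − 0.025^(1/N).

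| N | All events recorded | One missed | Fall in upper limit (points) |
|---|---|---|---|
| 50 | 1/50 = 2.0% (10.6%) | 0/50 = 0% (7.1%) | 3.5 |
| 50 | 2/50 = 4.0% (13.7%) | 1/50 = 2.0% (10.6%) | 3.1 |
| 55 | 1/55 = 1.8% (9.7%) | 0/55 = 0% (6.5%) | 3.2 |
| 55 | 2/55 = 3.6% (12.5%) | 1/55 = 1.8% (9.7%) | 2.8 |
| 55 | 5/55 = 9.1% (20.0%) | 4/55 = 7.3% (17.6%) | 2.4 |

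The rate falls by 1/55 = 1.8 to 1/50 = 2.0 points per missed case.

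**5. How likely such a case is.** The documents give no frequency. Let q be the assumed chance per subject that an implantation is abandoned with a major complication. The chance of at least one such case is 1 − (1 − q)^N. For q = 0.5% this is 22% (N = 50) to 24% (N = 55). For q = 1% it is 40% to 43%. For q = 2% it is 64% to 67%, but that value would make every event at the planned 2% rate an abandoned operation. Even then, the rate is affected only if the site follows the later start and the event is not recovered by another route.

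**The case against.** The strongest reply is that a site would have to set aside several other instructions to lose the event. Section 3.5.5.2 opens by sending timing questions to the schedule, which marks adverse-event reporting at surgery. That section also treats major complications and serious adverse events as one class. A major complication of an abandoned operation is therefore notifiable from consent, within 24 hours (4.5.13), on a form that 3.5.5.2 places in the electronic case report form, and it goes to the safety board (3.6.5). The sample-size text in 3.6.1.4 can be read as treating implantation as beginning with anesthesia, which would align the two starts. Much of this stands, and it makes a silent loss unlikely.

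It does not remove the conflict. Section 4.5.2 starts form recording of serious events, too, at implantation. Section 4.5.12 says that the serious-event form is not the adverse-event form. Nothing says that a notification made before implantation feeds SAP Table 9.1. The anesthesia reading is not applied to adverse-event collection anywhere, and the Full Analysis Set definition points the other way.

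A reader might infer that the causality restriction is what loses the event. It is not, as step 2 shows. A reader might also infer that sites following 3.5.5.2 would report almost no unrelated events. The documents do not support that: the relatedness phrase may qualify serious events only, neighbouring text asks for all complications and any suspected adverse event, and the adverse-event form has a box for unrelated events.

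**Conclusion.** The recording rules contradict each other and the safety set, and should be reconciled.

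- **Start.** A complication of an abandoned implantation could be left off the adverse-event form while its subject stays in the denominator. Any such loss would favour the device. It is tempting to conclude that this subject will be reported as event-free, or that the co-primary rate is biased. The documents show only that this could happen, given the schedule and the notification from consent. Nor do they show that the events at risk are the most serious ones.
- **Scope.** This is a separate inconsistency. It affects the all-adverse-event rate and the related against unrelated tabulation.
- **End.** The three end points differ, but no effect is shown on the co-primary endpoint, which concerns the first year of follow-up.

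The size is conditional: 1.8 to 2.0 points on the rate, and about 2.4 to 3.5 points on the exact upper limit, for each missed major complication in the cases tabulated. This assumes that at least one such case occurs and stays out of the analysis database.

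**What to change.** Replace the wording in protocol 2.4.1.2, 3.5.5.2 (Description) and 4.5.2, and in SAP 5.9, with one recording rule:

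- All adverse events, regardless of causality, are recorded on the case report form for every subject in the Safety Analysis Set.
- Recording starts no later than the start of the implantation procedure, counted from anesthesia.
- Subjects whose implantation was started and abandoned are expressly included.
- One end date is stated and used throughout.

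Before analysis, reconcile serious-event notifications against the analysis database for every subject in the Safety Analysis Set who is not in the Full Analysis Set. If collection has finished, this check can still be made through site queries.

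The cost is amendment wording, a form-completion note and a few more events to enter. Sample size and tests do not change. The reported rate may become slightly less favourable.

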### **Procedure for all complications**

Any suspected adverse event should be recorded on the “Adverse Event Report Form”, and the serious adverse event on the “Serious Adverse Event Report Form” available directly in the ECRF.

For each adverse event, the outcome must specified at the end of the study.

### **Procedure for explanted device**

Explanted device must be recorded on the “Explanted Device Report Form”

Every explanted device shall be tested to determine the reason for device failure, and device explantation shall be reported as a serious adverse event and classified according to AAMI-CDV-4 CI86 guideline.

All explanted devices shall be returned to Oticon Medical for a formal evaluation and a report shall be made according to the criteria specified in the AAMI-CDV-4 CI86 guideline. It will be the responsibility of the Oticon Medical Vigilance System to determine the final classification of the device failure. Concurrent with any reporting to Oticon Medical of an explant, a report shall also be sent to the Local Competent Authority having relevant jurisdiction.

Complications may lead to device explantation, in such cases initial SAE reporting shall specify the reason:

- a. Explantation due to unrelated medical reasons, for example:

Device is removed to enable diagnostic or therapeutic procedures for conditions unrelated to the implantation or function of the device (e.g. MRI scanning need outside manufacturer specification, radiotherapy, surgical resection, etc.)

- b. Explantation for medical reasons associated with the device.

Any device explanted with medical symptoms that could be related to the device and/or caused by device malfunction, for example:

- Meningitis secondary to the cochlear implantation
- Infection near the receiver/stimulator, lead and/or electrodes
- CSF leakage due to the occurrence of CSF leakage secondary to cochlear implantation.
- Skin flap complication secondary to the cochlear implantation
- Allergic reaction to device components
- Dizziness due to occurrence of balance and other vestibular-related issues
- Pain or discomfort that cannot be eliminated with changes in program parameter settings (e.g. deactivating an electrode).
- Tinnitus appearing during device use or an increase in pre-existing tinnitus
- Extra-cochlear stimulation, stimulation at sites outside the cochlea (e.g. facial nerve, chorda tympani, or return electrode placement, etc.) secondary to cochlear implantation and resulting from medical related factors (e.g. anatomical malformation, otosclerosis, cochlea ossification, etc.)
- Electrode array misplacement during cochlear implantation
- Electrode migration out of the cochlea
- Implant migration/extrusion
- Performance issue, the patient experienced a performance decline and/or failed to achieve a clinically-expected performance level attributable to health-related issues
- Change in patient behavior with the device use, such as refusing to wear the device
- Other; a patient may experience a sign or symptom not listed above or due to an unforeseen medical reason.

- c. Explantation because of suspected device failure.

This category is determined by in-vivo testing which confirm malfunctions. For example:

- Sudden loss of sound and/or gradual loss of function that occur over a short time
- Loss of all connectivity with the implant
- Shocking sensations, intermittent “popping” sounds, intermittent surges in loudness that exceed the loudness levels set by the clinician, and
- Intermittent or permanent changes in speech perception or reported sound quality
- Abnormal impedances accompanied by a change in sound quality
- Performance decline because of a loss of functional electrode channels
- Magnet issue/displacement
- Case damage
- Intermittent or unstable communication between internal and external components

## **Calculation**

The proportion of patients experiencing a specified events shall be tallied and calculated.

Complications shall be classified as major and minor according to the Cohen & Hoffman criteria [23].

### **3.5.5.3 Procedure to assess technical functionalities**

Impedance and ECAP measures will be performed per-operatively at the end of the surgery; at implant activation; at 3, 6 and 12 months post activation; and at unscheduled visit if available:

- Impedance helps to ensure the correct electrode/tissue contact, and the correct operation of the internal part. The test will takes 30 sec. or more if some electrodes impedance are out of range and need to be checked again.
- ECAP (Evoked Compound Action Potential) is the electrophysiological responses of the auditory nerve. The test will takes approximately 2 min (standard parameters: 4 electrodes stimulated, 6 measures and 50 repetitions per measures).

The impedance changes over time will be accessible from the patient maps in the fitting software. If any electrode turns out of range, it will be deactivated. Out of range electrode impedances can reflect degraded electrode-neuron interface, and can be related to electrical stimulation failure. Calculation: average of each electrode impedance at different time points and description of localization and number of electrode failures.

The ECAP is the synchronous whole auditory nerve activity in response to an electrical stimulus. This is commonly measured by the difference in amplitude between two peaks (N1 and P2), characteristic from the human auditory nerve response [44]. These delays suffer from variations among both CI users and devices but is situated among 0.3 and 0.6 msec.

Calculation: average of N1-P2 amplitude at each time point.

**3.5.5.4 Schedule of activities (Study Table)**

Protocol activity	V1	V2	V3	V4	V5	V6	V7	V8	Unscheduled visit(s) #
	8 weeks pre-surgery	4 weeks pre-surgery	Baseline	2 weeks post-surgery	1 month post-surgery	3 months post-activation	6 months post-activation	12 months post-activation	
	Screening	Inclusion	Surgery	Follow-up	Activation	Follow up	Follow up	End of study	NA
Week (-8)	Week (-4)	Week (0)	Week (+2) post-surgery	Month (+1) post-surgery	Month (+4) post-surgery	Month (+7) post-surgery	Month (+13) post-surgery	Month (+13) post-surgery	NA
Eligibility									
Informed consent	X*	X**							
Eligibility criteria		X							
Demographic data		X							
Medical and Hearing History		X							
Evaluations									
HINT-Q		X				X	X	X	
HINT-N		X				X	X	X	
Study device									
Surgery			X						
Implant activation					X				
Patient Diary									
Diary issued					X	X	X		
Diary returned					X	X	X	X	
Safety									
Adverse event reporting			X	X	X	X	X	X	X
Electrodes Impedance			X		X	X	X	X	(X)
ECAP			X		X	X	X	X	(X)
Concomitant medications		X	X	X	X	X	X	X	X

\*Informed consent given

\*\*Informed consent obtained

#unscheduled visits may occur in addition to the predefined protocol specific visits. Unscheduled consultations must be related to CI complications/adverse events and/or additional speech processor fittings. The PI may plan any unscheduled consultations as needed. Impedance and ECAP measurements are optional and depend on the nature of patient visit.

**3.5.6 Permitted visit window periods**

Visit	Visit interval (defined as number of weeks relative to visit 3, baseline)	Visit window (defined as number of days from previous visit indicated plus and/or minus day stated)	Visit window (defined as a range in days from previous visit indicated)
1	-8	NA	NA
2	-4	28 days from visit 1 (-25 to +14 days)	3-42 days from visit 1
3	0	28 days from visit 2 (+/- 14 days)	14-42 days from visit 2
4	+2	14 days from visit 3 (-7 to +6 days)	7-20 days from visit 3
5	+4	28 days from visit 3 (-3 to +6 days)	25-34 days from visit 3
6	+16	112 days from visit 3 (-7 to +6 days)	105-118 days from visit 3
7	+28	196 days from visit 3 (-7 to +6 days)	189-202 days from visit 3
8	+52	364 days from visit 3 (-7 to +6 days)	357-370 days from visit 3

